**Safety endpoints:**

All Patients:

- At LT (long term) weeks 104 and 156 height and weight measurements and derived BMI as  $\text{weight (kg)/height (m)}^2$ .

Patients with Secondary Hypertension:

- At LT weeks 104 and 156 renal function evaluation

**Other endpoints:**

- At LT weeks 104 and 156 neurocognitive evaluation for secondary hypertensive patients only

Patient demographics and relevant baseline characteristics will be obtained from the core study (CSPP100A2365) and summarized by actual treatment regimen at the end of study CSPP100A2365E1 (aliskiren vs. enalapril). Key measurements (weight, height, BMI and neurocognitive assessments), both raw values and their changes from baseline, will be summarized by visit (as recorded in the CRF) and treatment regimen. Safety observations will be summarized by treatment regimen.

Treatment regimen in this document refers to actual treatment regimen at the end of study CSPP100A2365E1 (aliskiren vs. enalapril)

Unless stated otherwise, baseline refers to the core study (CSPP100A2365) baseline.

Unless stated otherwise, statistical tests will be carried out at a two-sided significance level of 0.05 using SAS® statistical software (██████████) version 9.3 or higher.

**1.2.1 Population of analysis**

The **Enrolled to Follow-up Set (EFS)** will consist of all patients who sign the informed consent form for CSPP100A2365E2. Patients will be analyzed according to the treatment received in the CSPP100A2365E1 study.

**1.2.2 Protocol deviations**

A listing of protocol deviations will be produced by treatment regimen including the date and study day of the deviation occurrence.

**1.2.3 Medical history**

The number of patients with relevant medical history and/or continuing medical conditions collected at Week 2 (Visit 6) of the extension study (CSPP100A2365E1) and adverse events collected during the extension study (CSPP100A2365E1), regardless of whether they are resolved or on-going at the start of the CSPP100A2365E2, will be combined and summarized by primary system organ class, preferred term, and treatment regimen for the EFS. If there are

any on-going AEs in the CSPP100A2365E1 study which are on-going at the start of CSPP100A2365E2 and have changed in severity during CSPP100A2365E2, it is assumed that they will be reported as new AEs in CSPP100A2365E2.

#### **1.2.4 Baseline and demographic characteristics**

Patient demographics and baseline characteristics will be summarized by treatment regimen for the enrolled to follow-up set. Continuous variables will be summarized with descriptive statistics (n, mean, standard deviation, Q1, median, Q3, minimum, maximum). Categorical variables will be summarized with counts and percentages. In addition, all demographic and baseline data will be listed by patient and treatment regimen.

The demographic and baseline characteristics collected at Study CSPP100A2365 baseline (Visit 2) include:

##### Categorical variables:

- Age groups (6-11 years, 12-17 years, and 6 – 12 years, 13-17 years)
- Sex (Male, Female)
- Race (Caucasian, Asian, Black, Native American, Pacific Islander and Other)
- Ethnicity (Hispanic/Latino, Chinese, Indian (Indian subcontinent), Japanese, Mixed ethnicity and Other)
- Weight category ( $\geq 20$  kg and  $< 50$ kg,  $\geq 50$  kg and  $< 80$ kg,  $\geq 80$  kg and  $\leq 150$  kg)
- Hypertension etiology (primary, secondary)
- eGFR category ( $< 60$ ,  $\geq 60$  ml/min/SA and  $< 90$ ,  $\geq 90$  ml/min/SA)
- BMI category ( $< 95^{\text{th}}$  percentile and  $\geq 95^{\text{th}}$  percentile)

##### Continuous variables:

- Age (years), Height (cm), Weight (kg), BMI ( $\text{Kg}/\text{m}^2$ ), eGFR (ml/min/SA)
- msSBP (mmHg), msDBP (mmHg), sitting pulse (bpm), standing systolic/diastolic blood pressure (mmHg)

#### **1.2.5 Concomitant or prior medication**

Concomitant medications and significant non-drug therapies will be summarized with counts and percentages by treatment regimen for the EFS.

Concomitant medications from the extension study (CSPP100A2365E1), or from the original study CSPP100A2365 that stopped before the start of this study (CSPP100A2365E2) will be summarized as prior medications using counts and percentages by treatment regimen for the EFS.

#### **1.2.6 Analysis of primary variables**

The primary endpoints are the changes in weight, height, BMI and neurocognitive assessments from baseline to visit LT 18 for the EFS.

Baseline is defined as the baseline observation taken from the core CSPP100A2365 study. The changes from baseline in primary endpoints will be calculated as value at visit LT 18 – value at Baseline.

End of CSPP100A2365E2 study is visit LT 18 for the primary hypertension group and visit LT 19 for the secondary hypertension group. Visit LT 17 is end of study visit from CSPP100A2365E1 study.

The secondary endpoints are the changes in weight, height, BMI and neurocognitive assessments from baseline to end of study, by hypertension group.

The changes from baseline in secondary endpoints will be calculated as (value at the End of Study visit) – (value at Baseline).

#### Primary analysis

The primary analysis will be a superiority assessment of change in weight, height and BMI from baseline to visit LT 18. For the purpose of describing the analysis of primary variables, weight will be used to describe the analysis. Height and BMI will be analysed in exactly the same fashion as described for the weight in this section. The null hypothesis to be tested is that the mean change of weight at visit LT 18, in the aliskiren regimen is equal to that in the enalapril regimen, versus the alternative hypothesis that they are not equal:

H0:  $\mu_1 = \mu_2$  versus H1:  $\mu_1 \neq \mu_2$

Where  $\mu_1$  and  $\mu_2$  are the mean of the change in weight from baseline to visit LT 18, for aliskiren and enalapril, respectively. This hypothesis will be tested at a two-sided significance level of 0.05 using an analysis of covariance (ANCOVA) model with treatment regimen, region (US, Euro), age strata at baseline (6 to 11 years, 12 to 17 years), and hypertension etiology (primary, secondary) as factors, and with baseline weight as the baseline covariate (refer to appendix 1). The estimated change from baseline and the 95% confidence interval for  $\mu_1 - \mu_2$  will be presented. For the analysis of change in height, the baseline height will be included as the baseline covariate in the model. For the analysis of change in BMI, baseline BMI will be included as the baseline covariate in the model. Missing values will not be imputed.

No multiplicity adjustment will be performed.

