As the first direct renin inhibitor for the treatment of hypertension in adults, aliskiren is proposed for use in hypertensive children 6-17 years of age, as an alternative to currently available therapies. Aliskiren may offer a therapeutic profile distinct from that of ACE inhibitors and ARBs ([Frampton and Curran 2007](#)). The course of hypertension and the effects of antihypertensive medications in adolescents are not likely to differ from the course of the disease and the effects of antihypertensive medications in adults. The pediatric study for which this is an off-therapy follow-up will include a reasonable proportion of school-age, pre-pubertal children with at least 50% of the children being 6-11 years of age.

As the prevalence of hypertension in children increases ([Soroff, et al 2004](#)) treatment alternatives to those currently available will be of increasing significance. It is known that hypertension prevalence increases progressively with increased BMI and in the pediatric population hypertension is detectable in approximately 30% of overweight children ([NHLBI 12th Report, 2004](#)). Obesity is thought to be a major contributor to essential hypertension in school age children and adolescents ([Weinberger, et al 2008](#)). Primary essential hypertension in children is generally mild and associated with a positive family history of hypertension or

CVD and mild/moderate/severe obesity. Aliskiren may therefore be particularly important in children 6-17 years of age with essential hypertension since it has been shown to be of comparable efficacy in obese adult patients compared to those of normal body mass index (BMI) (Jensen, et al 2008).

In summary, the efficacy and tolerability of aliskiren alone or in combination with other agents are comparable to other commonly used antihypertensive medications in adults. Given the results reported with aliskiren in adults with hypertension, a similar efficacy and tolerability of aliskiren in children 6-17 years of age would be anticipated, providing an additional treatment option for children with hypertension.

This study is intended to evaluate the off-therapy long term growth and development of children 6 – 17 years old after exposure to aliskiren for at least one year in studies CSPP100A2365 and CSPP100A2365E1, and was developed to comply with the EMA Pediatric Committee Pediatric Investigational Plan (PIP).

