In study CSPP100A2365 the dose-response, efficacy and safety of aliskiren was evaluated in double-blind fashion over 8 weeks. Study CSPP100A2365E1 provided double blind evaluation of the long-term safety, tolerability and efficacy of aliskiren compared to enalapril in the same patient population.

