2.1 Primary objectives

- To evaluate the long term growth and development of pediatric hypertensive patients aged 6 – 17 years when treated previously with aliskiren

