3.1 Study design

This is a multicenter 52 to 104 week off-therapy extension to evaluate long-term growth and development in pediatric hypertensive patients 6 – 17 years of age at initiation of treatment with aliskiren in study CSPP100A2365. Eligible patients will continue to be stratified by age (6 – 11 years and 12 – 17 years) at study CSPP100A2365 baseline (Visit 2) and by etiology of hypertension (primary and secondary). Likewise, stratifications by weight group and region assigned in study CSPP100A2365 will remain.

Table 3-1 Study design

[figure not shown]
CSPP100A2365E2 LT Safety Follow-up		
Week 52 LT (end of study visit CSPP100A2365E1)	Week 104 LT	Week 156 LT
Day 365 (LT)	Day 730 (LT)	Day1095 (LT)
Visit 17*	Visit 18**	Visit 19***

* Long-term (LT) safety extension visit numbers continue from CSPP100A2365E1

** End of study for patients with primary hypertension

*** End of study for patients with secondary hypertension

Figure 3-1 Study design

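### All growth tests are relative to enalapril, and no planned output sets growth after aliskiren against what is expected for age and sex

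*SAP*

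**What the plan says.** The only objective (Protocol 2.1) is "To evaluate the long term growth and development of pediatric hypertensive patients aged 6 – 17 years when treated previously with aliskiren". It names no comparator.

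The SAP's Primary analysis paragraph reads: "The primary analysis will be a superiority assessment of change in weight, height and BMI from baseline to visit LT 18". The null hypothesis is equal mean change in the aliskiren and enalapril regimens. On alpha it says "This hypothesis will be tested at a two-sided significance level of 0.05", and then "No multiplicity adjustment will be performed". Regimen means what the patient was actually taking at the end of E1, and change is measured from the core-study baseline (SAP 1.2).

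Two further growth analyses are planned. One repeats the ANCOVA with LT 18 values carried forward from LT 17. The other repeats it at end of study within each hypertension group. Both estimate the same aliskiren–enalapril difference.

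Outside the tests, SAP 1.2.6.1 and Protocol 9.4.2 tabulate values and changes from baseline by regimen and visit. The variables are weight, height and derived BMI in their raw units. A BMI percentile appears only as a baseline category (SAP 1.2.4).

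**The concern.** An evaluation of growth in children who took a drug naturally asks whether they grew as children of their age and sex should. A difference between two active regimens answers another question: whether they grew differently from children on enalapril. If both regimens slowed growth equally, every planned test would behave as if neither had.

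The raw summaries cannot settle this, because a growing child gains height and weight whatever the drug does, and the normal gain depends on age and sex.

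The question is not idle. Protocol 1.1 reports reductions of 15–50% in weight gain early in treatment of juvenile rats, followed by gains slightly above controls. That signal was measured against control growth, and the planned human analysis has no such benchmark. The risk is that a non-significant difference is taken as reassurance about growth that it cannot give.

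**Working it through.** **Inputs from the documents.** Contrast: aliskiren minus enalapril. Two-sided alpha: 0.05. Model: regimen, region, age stratum, etiology and baseline value (SAP 1.2.6.1). Age: 6 to under 18 at core baseline. LT 18 is LT week 104 and LT 19 is LT week 156. Neither document gives a sample size, power, SD, margin or target difference, so there is no planned figure to reproduce.

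**Assumptions, for illustration only.** Effect of −2 kg on weight gain, residual SD 6 kg, 50, 100 or 150 patients per regimen, equal allocation.

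**Step 1: what the contrast measures.** Let m be the expected gain without any drug effect, and a and e the effects of the aliskiren and enalapril regimens. The test estimates (m + a) − (m + e) = a − e. If enalapril has a fraction s of the aliskiren effect, this is (1 − s)a:

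- s = 0: −2 kg, the full effect
- s = 0.5: −1 kg
- s = 1: 0 kg, whatever the size of a

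**Step 2: simulation of the SAP ANCOVA, 2,000 runs per case.**

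| Case | Mean estimated difference | Rejection at 50 / 100 / 150 per regimen |
|---|---|---|
| No effect in either regimen | −0.02 to 0.04 kg | 5.2% / 4.9% / 4.7% |
| −2 kg in both regimens | −0.02 to 0.01 kg | 5.0% / 5.0% / 4.8% |

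Monte Carlo error is about √(0.05 × 0.95 / 2000) = 0.5 percentage points, so the two rows cannot be told apart. The aliskiren group's own mean change nevertheless fell from about 9.35 to 7.35 kg.

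An effect confined to aliskiren would be visible to the test. With a 2 kg difference, power is Φ(2 / (6√(2/n)) − 1.96), which gives 0.39 / 0.65 / 0.82. The blind spot is the shared part only.

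**Step 3: can the raw summaries show the shared part?** Assume normal two-year height gains of 10–13 cm at school age and 0–1 cm in the late teens. Moving 10% of a group from one kind of patient to the other shifts the expected mean by 0.10 × (10 − 1) = 0.9 cm to 0.10 × (13 − 0) = 1.3 cm. A raw mean that is 1 cm lower could therefore be a drug effect or a modest difference in age mix. Without an expected value for each child, the table cannot distinguish them.

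**Step 4: age at the visits.** A patient just under 18 at core baseline is about 18 + 104/52 = 20 at LT 18. A patient with secondary hypertension is about 18 + 156/52 = 21 at LT 19. A growth reference may not extend that far, so a rule is needed.

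**The case against.** The strongest reply is that the objective is descriptive and the plan does describe: the aliskiren regimen's values and changes appear at every visit. Growth relative to enalapril is also a legitimate comparison, inherited from E1, which per Protocol 1.1 gave a "Study CSPP100A2365E1 provided double blind evaluation of the long-term safety, tolerability and efficacy of aliskiren compared to enalapril in the same patient population". An off-therapy extension cannot add an untreated group. All of this stands. A reader might infer that the objective goes unanswered; the documents do not support that. It is answered relative to enalapril, but not relative to expected growth.

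Other stronger readings also fail:

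- **The contrast is void because everyone began on aliskiren.** Protocol 3.1 describes patients by their age "at initiation of treatment with aliskiren in study CSPP100A2365", but the core design is not in these documents. Even if every patient took aliskiren for all 8 core weeks, an aliskiren-specific effect proportional to exposure would be diluted by only 8/60 = 13%, or 8/52 = 15% if LT weeks count from core baseline.
- **Both groups took a blocker of the same system, so effects must cancel.** The supplied text does not state enalapril's class or any effect of it on growth. Full cancellation is a possibility that the plan cannot exclude, not an established fact.
- **The comparator or exposure wording undermines the analysis.** Protocol 3.4 marks the comparator rationale as not applicable, which is understandable where no study drug is given. Protocol 1.1 describes follow-up "after exposure to aliskiren for at least one year in studies CSPP100A2365 and CSPP100A2365E1", which does not fit the enalapril regimen. Neither entry drives an analysis.
- **Standardised scores would detect a small shortfall.** With no sample size and no SD of score change, no precision can be claimed.

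It is also fair that drift in a standardised score would not prove a drug effect, since hypertensive children may drift for other reasons. That limits the added output to description. It does not make raw units equally informative.

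**Conclusion.** The point holds in a limited form. Every growth test is relative to enalapril, and an effect equal in both regimens leaves the test at its 5% error rate whatever the size of that effect. This is algebra and needs no assumption about mechanism. Whether such a shared effect exists is unknown from the documents.

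The within-regimen output is raw, so it cannot show whether growth after aliskiren is as expected for age and sex. The size of that gap in cm or kg cannot be derived from the documents; the illustrations rest on the stated assumptions.

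Neither document says that a non-significant result would be reported as absence of a growth effect, so that is a risk of interpretation, not a planned claim. With no margin or power stated, such a result would not show equality with enalapril either.

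**What to change.** Keep the primary ANCOVA and make these changes in SAP 1.2.6.1:

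1. Add, for each regimen, the change in age- and sex-standardised height, weight and BMI scores from core baseline to LT 17 and LT 18, and to LT 19 in secondary hypertension, with 95% confidence intervals. Label the output descriptive.
2. Name the growth reference, and state how patients above its upper age limit are handled.
3. State that the ANCOVA measures growth relative to enalapril, and that a non-significant difference does not exclude an effect common to both regimens.

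The cost is SAP wording, derived variables and a few tables. Height and weight are recorded at the visits, and age and sex come from the core study. This assumes that exact age at each visit can be derived, since the SAP lists age in years. The downsides are that one reference must serve patients from several regions, and that a change in score cannot be attributed to drug.

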Variable	Information used in the data analysis; derived directly or indirectly from data collected using specified assessments at specified timepoints

Protocol synopsis

Title of study: A multicenter, 52 to 104 week off-therapy extension study to evaluate the long term growth and development of pediatric hypertensive patients 6 – 17 years of age previously treated with aliskiren in studies CSPP100A2365 and/or CSPP100A2365E1

Purpose and rationale: The purpose of this 52 to 104 week off-therapy follow-up to studies CSPP100A2365 and CSPP100A2365E1 is to evaluate the long term growth and development of children 6 – 17 years old (6 to less than 18 years old at baseline in study CSPP100A2365) with hypertension (msSBP \geq 95th percentile for age, gender and height) at baseline in study CSPP100A2365, previously treated with aliskiren. Patients identified in study CSPP100A2365 to have primary hypertension will be followed for 52 weeks (1 year) after the completion of study CSPP100A2365E1. Patients identified in study CSPP100A2365 to have secondary hypertension will be followed for 104 weeks (2 years) after the completion of study CSPP100A2365E1. The assessment of growth and development through height and weight measurement will be performed on all patients for 52 weeks, after which patients with primary hypertension will complete. The assessment of patients with secondary hypertension will continue for an additional 52 weeks during which growth and development will continue to be assessed with added neurocognitive and renal function evaluations.

This study is in compliance with the EMA PIP Positive Opinion in support of the monotherapy registration of aliskiren for the treatment of hypertension in pediatric patients 6 – 17 years of age.

Objectives:

- To evaluate the long term growth and development of pediatric hypertensive patients 6 – 17 years of age when previously treated with aliskiren

Population: The study population will consist of male and female hypertensive pediatric patients who have completed the CSPP100A2365E1 protocol. These patients were 6 – 17 years old and had an msSBP \geq 95th percentile for age, gender and height at baseline (randomization) in study CSPP100A2365. Patients will continue to be stratified by CSPP100A2365 baseline weight, age, hypertension etiology and region. Centers from the US and EU participating in CSPP100A2365 and CSPP100A2365E1 will participate in this off-therapy follow-up.

Inclusion/Exclusion criteria:

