All patients are to have met entry inclusion and exclusion criteria for CSPP100A2365 and CSPP100A2365E1.

- Successful completion of the CSPP100A2365E1 protocol
- Written informed consent; patients who are eligible to participate in this long-term off-therapy extension and whose parent(s)/guardian (s) consent in writing to their doing so after the purpose and nature of this investigation has been clearly explained to them. An assent will be obtained for some patients depending upon their age, maturity, capacity for understanding, and the local requirements regarding assents. Written informed consent must be obtained before any assessment is performed.

Investigational and reference therapy:

- Investigational therapy: none
- Reference therapy: none

Study medication is not used in this trial.

Study design: This is a multicenter, 52 to 104 week off-therapy extension to evaluate long-term growth and development in pediatric hypertensive patients 6 – 17 years of age at initiation of treatment with aliskiren in study CSPP100A2365. Eligible patients will continue to be stratified by age (6 to 11 years and 12 to 17 years) at study CSPP100A2365 baseline (Visit 2) and by etiology of hypertension

(primary and secondary). Likewise, stratifications by weight group and region assigned at study CSPP100A2365 will remain.

Efficacy assessments: Not applicable.

Safety assessments:

- At LT weeks 104 and 156 height and weight measurements
- At LT weeks 104 and 156 renal function evaluation only in patients with secondary hypertension

Other assessments:

- At LT weeks 104 and 156 neurocognitive evaluation only in patients with secondary hypertension

Data analysis: Demographics and baseline characteristics, safety data (height, weight, derived BMI, laboratory evaluations, SAE) and other data as appropriate, will be summarized descriptively by treatment regimen from CSPP100A2365E1.

For the superiority assessment of change in weight, the null hypothesis to be tested is that the mean change of weight in the aliskiren regimen is equal to that in the enalapril regimen, versus the alternative hypothesis that they are not equal:

$H_0: \mu_1 = \mu_2$ versus $H_1: \mu_1 \neq \mu_2$

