The statistical test for change from baseline in weight will be performed using an analysis of covariance (ANCOVA) model with treatment regimen from CSPP10AE1, region (US, EU), age strata (6 to 11 years, 12 to 17 years), and hypertension etiology (primary, secondary) as factors, and with baseline weight as covariate. The statistical test will be made at two-sided significance level of 0.05. The 95% confidence interval will be provided.

Changes from baseline in height and derived BMI will be analyzed using the similar model.

1 Introduction

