9.4.2 Statistical model, hypothesis, and method of analysis

Descriptive statistics (n, mean, standard deviation, median, minimum and maximum) of baseline, post-baseline values and changes from baseline will be summarized by treatment regimen in CSPP100A2365E1 and visit for EFS.

For the superiority assessment of change in weight, the null hypothesis to be tested is that the mean change of weight in the aliskiren regimen is equal to that in the enalapril regimen, versus the alternative hypothesis that they are not equal:

$$H_0: \mu_1 = \mu_2 \text{ versus } H_1: \mu_1 \neq \mu_2$$

The statistical test for change from baseline in weight will be performed using an analysis of covariance (ANCOVA) model with treatment regimen, region (US, Euro), age strata (6 to 11 years, 12 to 17 years), and hypertension etiology (primary, secondary) as factors, and with baseline weight as covariate. The statistical test will be made at two-sided significance level of 0.05. The 95% confidence interval for the pairwise comparison will be provided.

Changes from baseline in height and derived BMI will be analyzed using the similar model.

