### **1.2 Statistical and analytical plans**

The purpose of this 52 to 104 week off-therapy follow-up to studies CSPP100A2365 and CSPP100A2365E1 is to evaluate the long-term growth and development of children 6 – 17 years old (6 to less than 18 years old at baseline in study CSPP100A2365) with hypertension (msSBP  $\geq$  95th percentile for age, gender and height) at baseline in study CSPP100A2365, previously treated with aliskiren. Patients identified in study CSPP100A2365 to have primary hypertension were followed for 52 weeks (1 year) after the completion of study CSPP100A2365E1 (aliskiren vs. enalapril). Patients identified in study CSPP100A2365 to have secondary hypertension were followed for 104 weeks (2 years) after the completion of study CSPP100A2365E1. The assessment of growth and development through height and weight measurement was performed on all patients for 52 weeks, after which patients with primary hypertension completed the study. The assessment of patients with secondary hypertension continued for an additional 52 weeks during which growth and development was continually assessed with added neurocognitive and renal function evaluations.

The study population consists of male and female hypertensive pediatric patients who have completed study CSPP100A2365E1. These patients were 6 – 17 years old and had an msSBP  $\geq$  95th percentile for age, gender and height at baseline (randomization) in study CSPP100A2365. Patients will continue to be stratified by CSPP100A2365 baseline weight at Visit 2, baseline age group, hypertension etiology (primary or secondary) and region. Centers (approximately 70) from the US, EU and ROW participating in CSPP100A2365 and CSPP100A2365E1 will participate in this off-therapy follow-up.

The follow up visits 52 and 104 weeks of the study follow up will be referred to as Week 104 and Week 156, respectively, in the CSPP100A2365E2 study documents and output.

The primary objective of the study is

- To evaluate the long term growth and development of pediatric hypertensive patients 6 – 17 years of age when previously treated with aliskiren.

This objective will be evaluated by assessing the following endpoints:

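### Does the two-level region factor in the primary ANCOVA leave rest-of-world (ROW) patients without a place in the model?

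*SAP*

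**What the plan says.** SAP section 1.2 describes the population this way: "Centers (approximately 70) from the US, EU and ROW participating in CSPP100A2365 and CSPP100A2365E1 will participate in this off-therapy follow-up". The sentence before it says that "Patients will continue to be stratified by CSPP100A2365 baseline weight at Visit 2, baseline age group, hypertension etiology (primary or secondary) and region".

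SAP 1.2.6.1, Primary analysis, lists the model factors as "treatment regimen, region (US, Euro), age strata at baseline (6 to 11 years, 12 to 17 years", followed by etiology, with the baseline value of the outcome as covariate. The sensitivity analysis repeats this model with LOCF from visit LT 17. The secondary analysis uses a similar model by hypertension group.

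The protocol's population and its model agree with each other. The synopsis and section 4 say "Centers from the US and EU participating in CSPP100A2365 and CSPP100A2365E1 will participate in this off-therapy follow-up". The synopsis model has "region (US, EU), age strata (6 to 11 years, 12 to 17 years), and hypertension etiology (primary, secondary) as factors", and section 9.4.2 has "treatment regimen, region (US, Euro), age strata (6 to 11 years, 12 to 17 years".

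On where region comes from, the synopsis says "stratifications by weight group and region assigned at study CSPP100A2365 will remain" and section 3.1 says "stratifications by weight group and region assigned in study CSPP100A2365 will remain". Section 6.2 says the same of the core-study strata in general.

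The analysis set in SAP 1.2.1 takes in everyone who consents to this extension, with no restriction by region. SAP Appendix 1 enters region as a class variable and neither lists nor recodes its levels.

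**The concern.** Read literally, the SAP widens the population to three groups of centres and keeps a two-level factor written for two. A ROW patient belongs to the analysis set but has no named level in the primary model. Two programmers could follow the text and fit different models: one with ROW as a third level, one with ROW merged into Europe. A third possibility is worse. If region were blank for ROW patients, PROC MIXED would drop them without comment.

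The factor enters the primary models for weight, height and BMI, their LOCF repeats and, if region is kept there, the models by hypertension group. That is 3 + 3 + (3 × 2) = 12 fits. If the coding could move the treatment comparison, leaving it open until the data are in hand would give the analyst a choice in the primary analysis.

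**Working it through.** The documents give no sample size, SD, effect size or ROW share, so there is no plan figure to reproduce. The check has two parts.

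**1. What the text fixes.**

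- *Source of the variable.* Region is not created in this study. It is the stratum assigned in the core study, and only patients who completed the core study and its first extension can enter (protocol 4.1 and 4.2). Each should already hold a recorded value.
- *Label.* The SAP uses EU for centre location and Euro for the model factor. The documents do not say whether Euro is a wider stratum that already takes in some ROW sites.
- *Code.* A class variable with no level list runs with two recorded levels or three.
- *Exclusion.* No passage tells anyone to leave out a ROW patient.

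The analyst therefore uses the recorded stratum. The only open question is whether it has two levels or three.

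**2. How much that question matters.**

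Assumed inputs: 1:1 allocation, residual SD 6 kg, non-ROW patients split evenly between US and EU, ROW share f, and 3,000 simulated trials per setting. The model has treatment, region, age stratum, etiology and baseline weight. Mean standard error (SE) of the treatment difference, in kg:

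| n | ROW gain | f | ROW own level | ROW pooled with EU | Pooled / own |
|---|---|---|---|---|---|
| 100 | same | 0.10 | 1.230 | 1.223 | 0.99 |
| 100 | 3 kg less | 0.30 | 1.232 | 1.250 | 1.01 |
| 150 | same | 0.10 | 0.996 | 0.993 | 1.00 |
| 150 | 3 kg less | 0.30 | 0.994 | 1.011 | 1.02 |
| 200 | same | 0.10 | 0.858 | 0.856 | 1.00 |
| 200 | 3 kg less | 0.30 | 0.856 | 0.871 | 1.02 |

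At n = 150 in the less favourable row, the 95% half-width is about 1.96 × 0.994 = 1.95 kg with ROW as its own level, and 1.96 × 1.011 = 1.98 kg pooled.

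*Systematic shift.* Pooling biases the treatment difference only if ROW patients differ in gain and are unevenly spread over the arms. To first order the shift is (gain difference) × (difference in ROW share) = 3 × 0.10 = 0.30 kg. The region factor absorbs part of it. The simulation at n = 150 gives 0.27, 0.25 and 0.24 kg for f = 0.10, 0.20 and 0.30, about a quarter of the SE.

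*Chance shift.* With the same 3 kg difference and no systematic imbalance, the mean shift is zero. In a single trial of 150 it varies with an SD of 0.17 to 0.21 kg, about a fifth of the SE.

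*Models by hypertension group.* With 20 to 40 patients (assumed) and no etiology term, the SE with ROW as its own level is 0.998 to 1.034 times the pooled SE.

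*Exclusion, for contrast.* If a share s of patients did drop out, the interval would widen by 1/√(1 − s): 1.054 at s = 0.10, 1.118 at 0.20 and 1.195 at 0.30. This is the one reading with a visible cost, and it is the one the plan gives no support to.

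**The case for a change.** The best case for a change is that a stated factor of the primary model should cover the population that the same SAP describes. Inheritance from the core study does not fully answer this, because neither document lists the core-study levels. SAP version 2.0.0 says it keeps in line with the protocol, yet ROW appears in neither protocol population statement. The baseline variables listed in SAP 1.2.4 do not include region, so a reader may not see how ROW patients are spread over the regimens. All of that is correct as a remark on documentation.

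A single data set can also be made to look alarming. In one simulated set of 200 patients, with ROW gain 3 kg higher, the estimate was 0.17 kg (SE 0.90) with three levels and 0.83 kg (SE 0.94) pooled, a shift of 0.67 kg before rounding (0.832 − 0.166 = 0.666). That is one draw with a regional effect built in. The repeated simulations give the typical size, which is far smaller.

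The last argument concerns the models by hypertension group, where a separate ROW level could be sparse. With 2 ROW patients among 30, the chance that both are in one regimen is 2 × C(15,2)/C(30,2) = 210/435 = 0.48. With 5 it is 0.04. When it happens, those patients inform the treatment contrast only through the covariate estimates. The cost in precision is slight, however, and does not support a minimum-count pooling rule. At n = 30 with no regional difference, the own-level to pooled SE ratio is 2.346/2.300 = 1.02 with about 3 ROW patients and 2.352/2.305 = 1.02 with about 6.

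**Conclusion.** The inconsistency stands as a matter of wording: SAP section 1.2 names ROW centres, the primary model names US and Euro, and the mapping is not written down. It does not make the planned analysis unsound. The sensible reading is to use the region stratum recorded in the core study for every patient. That follows from both documents, runs with the code as given and excludes nobody. Whether ROW then sits inside Euro or forms a third level changes the SE by about 2% at most. It shifts the estimate by roughly a fifth to a quarter of an SE even when ROW patients differ by 3 kg.

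These sizes rest on assumed inputs: 100 to 200 patients, a residual SD of 6 kg and a ROW share of 10% to 30%. They also assume that every patient has a recorded region, which eligibility through the core study makes likely but the documents do not show. No change to the plan is needed.
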